⁵³ A two-tailed t-test between the means of two independent samples with unequal variances was conducted for each of the covariates across trial arms, with standard assumptions (alpha = 0.05). The Wilcoxon Test was also used for a portion of the cases to verify these results.

⁵⁴ The covariates examined at Local Authority Level were: Proportion of Child Population (0-18) (2022 Mid-Year Estimates); Share of Population known to be eligible for Free School Meals (2022-23); Proportion of Children in Need (2023); Proportion of School Children Requiring SEN Support (2022-23); Proportion of Children Looked After (2023); Proportion of Children in Low Income Families (2022-23). For Westmorland and Furness, the data for Cumbria (the LA that contained it previously before it split on 01 April 2023) was used.

participants received the intervention and which did not). This, in addition to the a priori data analysis plan, will prevent bias being introduced during data analysis.

Participants

The trial aimed to recruit twelve local authorities to take part in the pilot, six intervention local authorities embedding systemic practice in keyworker teams, and six local authorities not embedding systemic practice.

Keyworkers will be practitioners working in local authorities' family support or early help services (including those in the Supporting Families Programme) providing support to a caseload of families within the timeframe of the pilot.

Participants will be families (parents/carers and their children/young people aged 8 and over) that meet the following criteria:

- A parent/carer who has a keyworker within the trial period. This will mainly include 'new' families; those that are referred and then supported by a keyworker within the pilot period. Keyworkers will have to work with a family for at least 10 weeks within the pilot period, as we want to evaluate families with ongoing contact with this service that would be expected to be influenced by the treatment.
- Parent/carer has one or more children aged 0-17 they have legal responsibility for at the point of referral.
- Child or young person 8 years old and over as outcome measures have not been adapt for children younger than 8 years old.

Exclusion criteria

Local authorities were not eligible for the pilot if they:

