Recruitment of families into the pilot study has the advantage of being determined by eligibility for support by keyworkers. As a result, all families supported by a keyworker within the trial period will be eligible to be included within the trial if they consent to take part when completing the Family Outcome Questionnaire. Keyworkers in both control and intervention local authorities will receive training and detailed guidance in administering the Family Outcome Questionnaire. They will also receive ongoing support from Coram as well as from their local authority systemic practitioner including refresher training and drop-in sessions for troubleshooting.

Sample size calculations

When using a mixture of initial and revised numbers of families supported by local authorities that expressed an interest in the pilot, we decided to consider only 75% of the reported figures in our calculations. Our reasoning behind this was that whilst local

authorities provided their caseloads, we want to be cautious when taking these numbers into our estimates, as the caseload numbers may contain errors or old data, may include inactive or ineligible cases, and may include cases that are inaccessible as part of an evaluation owing to practicalities such as families relocating.

We hence conservatively estimate that the systemic practice trained keyworkers would potentially be dealing with 7,766 families, of which 1,165 families would participate in our programme data collection at baseline. Based on our assumptions on trial attrition in the CONSORT, this would amount to an analysable sample of 560 families, which was used to estimate an MDES of 0.446. While the dropout has led to a potential imbalance between treatment and control (65%:35%), this has been accounted for in our power calculations. We feel that this MDES is sufficient to detect a significant change using the GBO, with studies showing effect sizes^{55,56,57,58,59}

Table 2: Sample size calculations

| Parameter | Value |
|---------------------------------------|--|
| Minimum Detectable Effect Size (MDES) | 0.446 |
| Pre-test/ post-test correlations | Level 1 (participant): 0.6 Level 2 (family): 0.6 Level 3 (LA): 0.6 |
| Intraclass correlations (ICCs) | Level 2 (family): 0.3 Level 3 (LA): 0.1 |
| Alpha | 0.05 |

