| Number of families ⁶⁰ | Intervention: 361 Control: 199 Total: 560 |
| Number of participants | Intervention: 369 adults, 193 children Control: 203 adults, 101 children Total: 572 adults, 294 children |

⁶⁰ Final numbers reported (post attrition) that we will be analysing, rather than in the entire sample.

Updated sampling calculation (LAs = 10) – Only SF sample and latest assumptions

[figure not shown]

Figure 3 – Sampling calculations

SF Sample Size Calculation Table

| | |
|--------------------------------|------------|
| MDES | 0.446 |
| Alpha Level (α) | 0.05 |
| Two-tailed or One-tailed Test? | Two-tailed |
| Power (1- β) | 0.8 |
| Baseline/Endline correlations | |
| Individuals | 0.6 |
| Families | 0.6 |
| Local authorities | 0.6 |
| Average cluster size | |
| Individuals in families | 1.5 |
| Families in local authorities | 56 |
| Number of local authorities | 10 |
| Intraclass cluster correlation | |
| Families | 0.3 |
| Local authorities | 0.1 |

Assumptions

- 3 level clustering – individual in family in local authority
- Assumed a low ICC for families in terms of family functioning (expect different views)
- Assumed a very low ICC for local authorities in terms of family functioning (some clustering of scores based on shared factors, but not strong)
- Assumed baseline/endline correlations of 0.6 at all levels (unknown)

Figure 4 – SF Sample size calculation table

Outcome measures

Table 3: Primary outcome measures

| Variable | Progress towards personal goals |
|------------|--|
| Measure | Goal Based Outcomes (GBO) ⁶¹ |
| Sample | Parents/carers and children/young people aged 8 and over. The GBO will be administered as part of the Family Outcome Questionnaire at an individual level by keyworkers. There will be an adult version (for use with adults and young people aged over 12) and a child-friendly version (for use with children aged 8 to 12). Total GBO scores will be reported, as well as themed scores. We anticipate theming goals using existing taxonomies from psychotherapy research ^{62,63} and using inductive analysis owing to the novel context for use of the GBO. |
| Time point | Baseline: within the assessment period of the first six weeks of the keyworker working with a family. Midline: at a review point when working with the family. Typically, this is between two to five months of working with the family. Endline: At closure when the keyworker stops working with a family. |

Secondary outcome measures for families:

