Table 6: Secondary outcome for families 3

| | |
|----------|-----------------------------------|
| Variable | Step-up to children's social care |
|----------|-----------------------------------|

| | |
|------------|---|
| Measure | Reasons for closure (local authority closure assessment) “Step up/escalated to statutory children’s services” [binary yes/no]. |
| Sample | Families where keyworker support is ending. |
| Time point | Endline: At closure when the keyworker stops working with a family |

Table 7: Secondary outcome for families 4

| | |
|------------|--|
| Variable | Positive progress made by families at closure |
| Measure | Reasons for closure (local authority closure assessment) “End of casework, positive progress made against all issues” |
| Sample | Families where keyworker support is ending. |
| Time point | Endline: At closure when the keyworker stops working with a family. |

Table 8: Secondary outcome for keyworkers 1

| | |
|------------|--|
| Variable | Professional Wellbeing |
| Measure | Adapted measure of professional wellbeing using Professional Wellbeing Self-Assessment Tool ⁶⁶ and The Social Work Organisational Resilience Diagnostic (SWORD) Tool ⁶⁷ |
| Sample | Keyworkers who are in the pilot |
| Time point | Baseline: at the start of the pilot. For intervention local authorities this will be before the training begins. For control local authorities this will be after they have been trained in use of the family level outcome measures at the start of the pilot. Endline: At the end of the pilot. |

Table 9: Secondary outcome for keyworkers 2

| | |
|------------|--|
| Variable | Practice Quality |
| Measure | Adapted measure of practice using the Systemic Therapy Inventory of Change (STIC) and the Systemic Practice Competency Scale (SPCS) |
| Sample | Keyworkers who are in the pilot |
| Time point | Baseline: at the start of the pilot. For intervention local authorities this will be before the training begins. For control local authorities this will be after they have been trained in use of the family level outcome measures at the start of the pilot. Endline: At the end of the pilot. |

Primary outcome measure

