Unfortunately, no validated measure of either was identified. As a result, a set of questions were created to assess systemic practice quality based on the Systemic Therapy Inventory of Change (STIC), and the Systemic Practice Competency Scale (SPCS).

The Systemic Therapy Inventory of Change (STIC) is a multisystemic and multidimensional feedback system that provides therapists feedback about systemic domains of client change in individual, couple, and family therapy over time.

The Systemic Practice Competency Scale (SPCS) provides a structure for the assessment of Systemic Family Practice (SFP) skills to evaluate family therapy sessions as well as training and supervision. It covers 12 areas of systemic family practice: Interpersonal Effectiveness and Development of Therapeutic Alliance; Convening and managing the session; Collaboration; Conveying a Systemic View; Conceptual Integration; Use of Questioning; Feedback; Intervening in Process; Working with Power and difference; Exploring and managing emotions in sessions; Use of change techniques; and incorporating the outside World.

Data collection

Family Outcome Questionnaire

Data for the primary outcome measure (the Goal Based Outcome) and the first two secondary outcome measures (SCORE-15 and CARE measure) will be collected directly from families via an online Family Outcome Questionnaire administered by their keyworker in control and intervention local authorities. All families who are referred to keyworker teams for family support or early help within the timeframe of the pilot will be asked to complete the questionnaire by their keyworker. The questionnaire will form part of the standard assessment, review and closure process with families that keyworkers go through. Families and they will be supported to complete the questionnaire by their keyworker.

Baseline scores will be collected in the assessment period (first six weeks) when the keyworker starts working with a family. Midline scores (at least one) will be collected at a review point. Typically this is between two to five months of working with the family. Endline scores will be collected at closure when the keyworker stops working with a

family, or when the trial ends. Keyworkers will need to work with a family for a minimum of 10 weeks to be included in the trial analysis.

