As a minimum, at least one parent/carer and the child will need to complete the questionnaire at least two timepoints: baseline and at mid or endline. Ideally, all family members (including other carers and children) working with the keyworker will also complete the questionnaire. Keyworkers judgement will be used when deciding whether the child or young person is capable of completing the questionnaire. Versions of each measure have been developed for children aged 8 and over.

The questionnaire will be available online using a link provided to keyworkers, as well as paper versions for practitioners or administrators to upload. All families in the trial will be provided with an easy-read sheet on the outcome measures as part of their privacy notices and online consent form within the outcome questionnaire.

Training, guidance and support will be provided to keyworkers and those supporting data collection in the local authorities. Refresher training and ongoing support will be provided by Coram and the local systemic practitioner. The Family Outcome Questionnaire is included in Annex B.

Supporting Families Data collection

Data for two secondary outcome measures (whether a family has been stepped-up into statutory support and whether a family has been closed with positive progress as part of the Supporting Families Programme) will be collected indirectly from families through data local authorities collect as part of their early help data collection as part of the Supporting Families Programme. Families will consent to this data being provided via their consent forms and local authorities will provide this data as part of the Data Sharing Agreement agreed with each local authority.

To minimise the burden on families and keyworkers and to maximise the analysis that can be undertaken, local authorities will also be asked to provide additional data on the families already collect this data as part of their case management systems provided via DfE's early help dataset.

This additional data is currently being collected at two time points by local authorities:

- 1) In the assessment period when the keyworker first starts to work with a family usually within the first six weeks of working with a family.
- 2) At closure when the keyworker stops working with a family.

Baseline data will include demographic information on:

- Child Date of Birth

- Parent/carers Date of Birth
- Relationship of the parent/carer to the child
- Sex of the child

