Analysis will include a baseline description of the trial participants using baseline outcomes data and additional data provided by local authorities (see data collection above) and additional monitoring data from local authorities and IFT on fidelity as set out above. Descriptive statistics (means and standard deviations for continuous variables, percentages and counts for categorical variables) for each variable will be set out.

Outcomes analysis for the pilot study will include all randomised participants who provide outcome data across the pilot. Reporting will include participant flow throughout the trial, including completion rates of outcomes in a CONSORT diagram.

All outcomes will be analysed on an **intention-to-treat** basis meaning that all participants will be analysed according to the trial arm to which they were assigned, as opposed to whether the intervention was received.

We will calculate and report descriptive statistics, including the characteristics of the intervention and control groups on each key variable collected. We will carry out balance checks to report on how balanced the characteristics of respondents are across treatment and control groups. These characteristics will include the child/young person and parent/carers sex, age, ethnicity, English as an additional language, in addition to the child SEND status, child social care status, parent/carer disability, and parent/carer employment status.

Using this data, balance checks will be carried out to report on how balanced the characteristics of respondents are across treatment and control arms. For continuous variables (e.g. age), test balance will be undertaken using two sample t-tests with unequal variances. Balance in proportions (e.g. sex, ethnicity) will be tested using a chi-square test.

If any characteristics are significantly unbalanced between trial arms, these will be adjusted in the outcomes analysis. Analysis will report on full baseline characteristics of the sample including baseline outcome scores, the characteristics of those lost to follow-up, and the characteristics of the analysable sample. This will include the extent and pattern of missing data and explore this using regression modelling if required.

Missing data will be assessed to explore whether the data is:

- 1) *missing completely at random* (data is randomly distributed across the variable and unrelated to other variables),

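### The 10-week support rule excludes families on something seen only after allocation, contradicts the stated analysis set, and can remove events that the step-up and positive-closure outcomes count

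*Protocol*

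**What the plan says.** The 10-week rule appears twice in the protocol:

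- **Data collection, Family Outcome Questionnaire:** "Keyworkers will need to work with a family for a minimum of 10 weeks to be included in the trial analysis".
- **Participants:** "Keyworkers will have to work with a family for at least 10 weeks within the pilot period", because "we want to evaluate families with ongoing contact with this service that would be expected to be influenced by the treatment".

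Two other sections describe a wider set:

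- **Recruitment:** "all families supported by a keyworker within the trial period will be eligible to be included within the trial", subject to consent.
- **Impact evaluation, Analysis:** the outcomes analysis takes in all randomised participants with outcome data. It is called intention-to-treat, in the sense that "all participants will be analysed according to the trial arm to which they were assigned", whether or not the intervention was received.

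Tables 6 and 7 define step-up and positive progress at closure. Both give the sample as "Families where keyworker support is ending", with no minimum duration. The data come from the local authorities' early help records, not from the questionnaire.

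On respondents, the questionnaire section says "As a minimum, at least one parent/carer and the child will need to complete the questionnaire at least two timepoints". It then leaves the keyworker to judge whether the child is capable. Table 2 plans 560 analysed families and gives the participants as "Total: 572 adults, 294 children". Footnote 60 says these are post-attrition numbers for analysis.

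**The concern.** Weeks of support is not a baseline characteristic. It is observed after the local authority has been allocated, and the intervention could change it: the theory of change expects keyworkers to identify needs and engage families better, which could plausibly alter when a case closes or escalates. A set defined by surviving 10 weeks of support can therefore differ between arms even if the intervention has no effect on outcomes.

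The problem is sharpest for secondary outcomes 3 and 4. Step-up and positive closure are themselves ways in which support ends. A family escalated at week 6 is a step-up event under Table 6, but it is outside the analysis under the 10-week rule. Counting only closed cases selects on duration again: families still open at the end leave the denominator, so an arm that closes cases more slowly has a different denominator for the same number of events.

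For the primary outcome, the conflict leaves it undecided whether a family with a baseline at week 3 and a closure questionnaire at week 8 is analysed.

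**Working it through.** **1. The provisions side by side**

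| Provision | Family with baseline at week 3, stepped up and closing questionnaire at week 8 |
|---|---|
| Recruitment (all supported, consenting families) | In |
| Analysis (randomised, with outcome data) | In |
| Table 6 (support ending) | In, counted as an event |
| Participants (10 weeks) | Out |
| Data collection (10 weeks) | Out |

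These cannot all be followed.

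**2. Timeline.** Annex A runs baseline collection to February 2026 and ends follow-up at the end of April 2026. Counting 70 days back from 30 April gives 19 February. A family opened after that date cannot reach 10 weeks by then, so if baselines run to the end of the month some enrolled families fail the rule by design.

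**3. What the rule could do to the step-up outcome.** The protocol gives no step-up rate and no timing, so these inputs are assumptions: true step-up p = 15% in both arms, and a fraction e of step-ups before week 10. For simplicity only early step-ups are removed.

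Analysed rate = p(1 − e) / (1 − p·e)

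- e = 50%: 0.075 / 0.925 = 8.1%
- e = 30%: 0.105 / 0.955 = 11.0%

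| Early fraction, intervention v control | Analysed rates | Risk ratio with no true effect |
|---|---|---|
| 50% v 30% | 8.1% v 11.0% | 0.74 |
| 30% v 50% | 11.0% v 8.1% | 1.36 |
| equal | equal | 1.00 |

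**4. Parent-and-child minimum against Table 2.** Families with a child respondent cannot exceed the number of children:

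- Overall: at most 294 of 560 (52.5%), so at least 266 (47.5%) have none.
- Intervention: at least 361 − 193 = 168 of 361 (46.5%).
- Control: at least 199 − 101 = 98 of 199 (49.2%).

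These are minimum losses under a strict reading. They grow if responding families average more than one child.

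**5. Effect of a strict reading on the MDES.** For a three-level design with treatment at local authority level:

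MDES = (t[0.975, df] + t[0.80, df]) × √{[ρ3(1−R²)/K + ρ2(1−R²)/(JK) + (1−ρ2−ρ3)(1−R²)/(nJK)] / [P(1−P)]}

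Inputs from Table 2 are K = 10, J = 56, n = 1.5, ρ3 = 0.1 and ρ2 = 0.3. P = 0.6 is the 6:4 split of authorities. I take df = 7 and enter 0.6 as R², because this reproduces the stated figure:

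- Plan: (0.004 + 0.000214 + 0.000286) / 0.24 = 0.01875. The square root is 0.1369, and × 3.261 gives 0.4465 (stated: 0.446).
- With 294 families and 2.02 respondents each (572/560 = 1.02 adults plus one child): (0.004 + 0.000408 + 0.000404) / 0.24 = 0.02005. The square root is 0.1416, and × 3.261 gives 0.462.

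The local authority term dominates; even with unlimited families the MDES is 0.421. With 0.6 treated as a correlation (R² = 0.36) the change is 0.565 to 0.584, equally small. Which R² is right is a separate question.

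**The case against.** **The intention-to-treat analysis is not broken.** The protocol defines it as analysis by assigned arm, and the 10-week rule moves no family between arms. The rule is also disclosed, with a reason. This stands as far as it goes: a reader might infer that arm assignment is violated, and the text does not support that. The conflict is about who is included. But the stated reason is likely exposure to treatment, which sits badly with analysis regardless of receipt, and disclosure does not remove selection.

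**Consent and questionnaire response also come after allocation.** True, and the proposed set still depends on both. That limitation remains, but it is no reason to add a further condition tied directly to two outcomes.

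**The rule may not apply to the administrative outcomes.** It sits under the questionnaire heading, and Tables 6 and 7 set no limit. That reading is possible. However, the Participants section applies 10 weeks as a general criterion, and the rule's own wording refers to the trial analysis without restriction. The text has to say which is meant.

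**Nearly half the families are not lost.** A reader might infer that the parent-and-child minimum removes 266 families. The documents do not support this. It is worded as a collection minimum with a capability qualifier, the Participants section admits carers of children aged 0–17, and Table 2 with footnote 60 plans to analyse families without a child respondent. The 47.5% is a floor under a strict reading that the plan's own numbers contradict.

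**The SAP may settle this.** It may, but the protocol already states rules that conflict.

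**Conclusion.** The concern holds for the 10-week rule. It is a post-allocation exclusion that contradicts the Recruitment and Analysis sections. Applied as written to step-up and positive closure, it removes some of the events those outcomes count, and the closed-case denominator adds a second selection by duration.

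The size and direction of any bias cannot be determined from the protocol. The risk ratios of 0.74, 1.36 and 1.00 show the mechanism under assumed rates. None is a forecast, and it would be wrong to infer that the rule favours the intervention. Nor is there any figure for how many families have under 10 weeks of support. The 560 is already post-attrition, so some of that loss may be included in it.

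The parent-and-child minimum is a wording point. Even a strict reading would take the MDES only from 0.446 to about 0.462. The harm at issue is selection and an undefined analysis population, not power.

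**What to change.** 1. **Questionnaire outcomes.** Define the primary analysis set as every consenting family with a baseline and at least one follow-up score, whatever the weeks of support. Amend Participants and Data collection to agree with Recruitment and Analysis.
2. **Step-up and positive closure.** Include every consenting family opened in the window, closed or not. Use either a fixed follow-up window that every included family can complete, or a time-to-event analysis with open cases censored. Report follow-up time by arm. Simply counting open cases as no event is not adequate: families opened in February 2026 have only about 9 to 13 weeks to the end of April (61 to 88 days).
3. **Sensitivity analysis.** Keep at least 10 weeks of support as a sensitivity analysis for the family outcomes.
4. **Respondents.** Reword the parent-and-child minimum as a collection target, and state that a family with one eligible respondent is analysed.

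The cost is a short protocol amendment, matching SAP wording and probably one added data field. The closure data listed in the protocol give the reason and outcome but no closure date, which item 2 needs. The date would also help item 3, because the questionnaire's duration bands include 9 to 12 weeks, which straddles the threshold. The statistical downside is small: some minimally exposed families will dilute the estimate, and the sensitivity analysis will show by how much.

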- 2) *missing at random* (data is not randomly distributed but they are accounted for by other observed variables), or
- 3) *missing not at random* (data systematically differs from the observed values) and adjust our approach to analysis based on this assessment.

Where data is missing completely at random, no imputation will be carried out and only available cases will be analysed. Where data is missing at random it will be considered whether multiple imputation is required. Where data is missing not at random it will be considered which sensitivity analyses are required to produce estimates that adjust for missingness.

We anticipate all variables will be analysed using a three-level multilevel modelling approach for family-based outcomes, and two-level multilevel modelling approach for keyworker outcomes to estimate the average effect of the treatment allocation using a Huber-White (HW) robust error procedure to account for heteroscedasticity. We anticipate including fixed effects for delivery site and time from randomisation (to account for ongoing referral throughout the pilot). We will also adjust for stratification factors used at randomisation and report ICCs for clustering. The coefficient will be an estimate of the size and direction of the treatment effect and its significance will be tested with a two-tailed 5% Type I error threshold.

The analysis explore the influence of trial arm allocation compliance using Complier Average Causal Effect Analysis, by including intervention receipt in an instrumental variable analysis. The analysis will also include an exploratory analysis with sub-groups or other exploratory analysis including analysis of harms.

All analysis will adhere to good spreadsheet design principles and document the sequence of steps used to get from raw data to findings to enable review. All data cleaning and analysis will be undertaken in R statistical software. All code and analysis will be quality assured by a second member of staff and includes both the logic and the arithmetic of analysis. Full records of code will be shared with the DfE and published to enable replication.

Implementation and process evaluation

The aim of the Implementation and process evaluation (IPE) will be to address key questions of implementation and delivery including fidelity, dosage and quality, reach and responsiveness, acceptability as well as mechanisms of change, barriers and enablers to implementation and capacity and capability to implement.

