- If there are more than 6 'stop' criteria met, we will recommend not proceeding to a full trial

⁹⁸ Avery K., et al (2017) Informing efficient randomised controlled trials: exploration of challenges in developing progression criteria for internal pilot studies. *BMJ Open*. doi: 10.1136/bmjopen-2016-013537.

Table 13: Criteria for full-scale trial

| Criteria | Green (proceed) | Amber (review) | Red (stop) |
|---|--|--|---|
| 1. Adequate recruitment of local authorities into the trial | ≥10 local authorities recruited | ≥8 local authorities recruited | <5 local authorities recruited |
| 2. Adequate retention of local authorities within the trial (an indicator of acceptability of randomisation) | No local authorities drop out of the trial | 1-3 local authorities drop out of the trial | ≥4 local authorities drop out of the trial |
| 3. Adequate recruitment rate of families into the trial and completion of baseline Family Outcome Questionnaire | 80-100% (n=932-1165) families complete baseline measures | 60-79% (n=699-931) families complete baseline measures | 0-59% (n=0-698) families complete baseline measures |
| 4. Adequate response/attrition rate to the trial | 50-100% families complete endline measures | 35-49% families complete endline measures | 0-34% families complete endline measures |
| 5. Adequate follow-up data from the keyworker survey | ≥200 keyworker follow-up measures completed | ≥175 keyworker follow-up measures completed | <150 keyworker follow-up measures completed |
| 6. Minimal Family Outcome Questionnaire data loss/unusable due to poor quality data | 10% of outcome data lost to poor quality data | 15% of outcome data lost to poor quality data | 20% of outcome data lost to poor quality data |

| Criteria | Green (proceed) | Amber (review) | Red (stop) |
|--|--|--|---|
| 7. Sufficient administrative data on families collected from local authorities to allow for analysis | Low rates of missing administrative data (>75% of family cases complete) | Some missing data (>60% of cases complete) | High rates of missing data (<50% of cases complete) |
| 8. Evidence of promise according to the primary outcome of progression towards goals | The MDES of the study is ≤ 0.50 | The MDES of the study is between 0.51-1 | The MDES of the study is > 1 |

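### The missing-data plan makes sensitivity analysis depend on classifying the data as MCAR, MAR or MNAR, which observed data cannot settle, while about 52% of baseline families are not expected to reach analysis

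*Protocol*

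**What the plan says.** The Analysis section of the impact evaluation begins its missing-data plan with a diagnosis: "Missing data will be assessed to explore whether the data is" MCAR, MAR or MNAR. It then says the analysis will be adjusted to the result. Three branches follow.

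- **MCAR:** "Where data is missing completely at random, no imputation will be carried out and only available cases will be analysed".
- **MAR:** the team will consider whether multiple imputation is needed.
- **MNAR:** "Where data is missing not at random it will be considered which sensitivity analyses are required".

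No missing-data sensitivity analysis is promised whatever the classification. The same section does commit to reporting the characteristics of those lost to follow-up and the extent and pattern of missingness, with regression modelling if needed. It also announces a final statistical analysis plan (SAP) before any analysis.

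On scale, Sample size calculations gives a number of families, "of which 1,165 families would participate in our programme data collection at baseline", and after the assumed attrition "this would amount to an analysable sample of 560 families". Table 2 splits these as "Intervention: 361 Control: 199 Total: 560", and its footnote describes them as "Final numbers reported (post attrition) that we will be analysing, rather than in the entire sample". Table 13 uses the same baseline denominator: "80-100% (n=932-1165) families complete baseline measures".

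**The concern.** The branch taken depends on a fact that the data do not contain. If missingness is related to observed variables, MCAR can be ruled out. If no such relation is found, MCAR has not been shown, because missingness may still depend on the unseen outcome. MAR and MNAR differ only in how missingness relates to unobserved values, so no analysis of the observed scores can tell them apart. An analyst who follows the rule in good faith could settle on MCAR or MAR and report a result with no check on the assumption behind it.

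Outcome-related loss is plausible here. The trial is unblinded. Keyworkers administer the questionnaire, help families complete it, and judge whether a child is able to. Endline falls at case closure or at the end of the trial. Completion may therefore follow engagement or progress, and may do so differently by arm. The estimate has consequences: indicative impact is one of the two primary aims, the effect gets a two-tailed 5% test, and promise of impact is one of the questions put to the full-trial decision.

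**Working it through.** **1. Share not reaching analysis.** Inputs: 1,165 baseline families and 560 analysable (Sample size calculations, Table 2).

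- 361 + 199 = 560, so the arm figures agree with the total.
- 1,165 − 560 = 605, and 605 / 1,165 = 0.519. Retention is 0.481.

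The 52% is derived; the protocol does not print it. No attrition by arm is stated.

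**2. The yardstick.** The planned minimum detectable effect size (MDES) of 0.446 can be reproduced with the standard three-level cluster formula: 10 authorities, 56 families per authority, 1.5 individuals per family, intraclass correlations of 0.3 (family) and 0.1 (authority), 60% of authorities in the intervention arm, 7 degrees of freedom, and 0.6 entered as the share of variance explained.

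- Variance term: 0.4 / (0.6 × 0.4 × 10) × (0.1 + 0.3/56 + 0.6/84) = 0.1667 × 0.1125 = 0.01875.
- Multiplier: 2.365 + 0.896 = 3.261.
- MDES: 3.261 × √0.01875 = 0.4465.

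It is used below only for scale.

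**3. Can the observed data pick the branch?**

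| Question | What observed data can do |
|---|---|
| Is it MCAR? | Contradict it; not establish it |
| MAR or MNAR? | Not separate them |

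A simulation under assumed conditions shows the first row. It had 1,165 families, about 48% observed, no clustering, a true effect of zero, a baseline–endline correlation of 0.6, and missingness that depended on the unobserved part of the outcome in the intervention arm only. Over 1,000 runs, a check of missingness against baseline score and arm rejected MCAR in 5.0% of runs, its nominal rate. The available-case estimate, adjusted for baseline, was biased by 0.23 SD. The check was chosen for the simulation; the protocol names none.

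**4. Size of possible bias (illustration).** Let f be the share of intervention families with missing outcomes, and δ the amount in SD by which they fall below what the observed data predict, with no such departure in control. The effect is then overstated by f × δ. The values of δ are assumptions with no source in the protocol.

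| f | δ | Bias (SD) | Share of 0.446 |
|---|---|---|---|
| 0.519 | 0.2 | 0.104 | 23% |
| 0.519 | 0.4 | 0.208 | 47% |
| 0.26 (half) | 0.2 | 0.052 | 12% |
| 0.26 (half) | 0.4 | 0.104 | 23% |

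The first two rows apply the pooled 52% to the intervention arm and treat every family not analysed as a missing outcome. The last two show the proportionate reduction if only half are.

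**The case against.** **This belongs in the SAP.** Two of the three branches are openly provisional, and delta ranges or tipping points are ordinary SAP content. That stands for the detail. It does not cover the structure: the protocol already makes the method depend on a classification and places sensitivity analysis on one branch. A SAP that follows it inherits the fault, and one that departs from it must override the protocol.

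**No test is named.** A reader might infer that a non-significant MCAR test sends the trial to available cases. The text speaks only of an exploratory assessment and gives no test or threshold. The weakness lies in the classification, however it is made.

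**The MNAR branch is reachable.** A reader might infer that it can never be entered. That is too strong. MNAR can be judged on substantive grounds, and local authority closure data (reason for closure, outcome at closure) may show how some families without endline scores fared. Such evidence informs the judgement but cannot settle it.

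**Not all 605 are dropouts.** A reader might infer that more than half of families will have missing outcomes. The document does not show this. Families supported for under 10 weeks are excluded, and inclusion requires questionnaires at two timepoints. The flow figure is not shown, so the split is unknown. The 560 may also include families with midline only.

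**Available cases need not mean relying on MCAR.** A likelihood-based multilevel model can be valid under MAR given its covariates. That is correct, and it is why the remedy keeps the planned model. MAR is just as untestable, which is why the sensitivity analysis should be unconditional.

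**It is a pilot.** The aim is indicative evidence, and the risk table ranks power below feasibility. This limits the severity, but a biased estimate could still mislead the decision on a full trial.

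**Conclusion.** The point holds as a fault in a stated rule. Sensitivity analysis is tied to a classification that observed data cannot deliver, so following the protocol can leave a biased estimate unchecked. The planned figures imply that 605 of 1,165 families (52%) do not reach analysis, with an unknown part of that due to inclusion rules. The 0.10 to 0.21 SD range is not a forecast. It rests on the assumed 0.2 to 0.4 SD departure in the intervention arm alone, on the pooled loss applying to that arm, and on all of it being missing outcomes; it shrinks in proportion if fewer are. The logic of the fault does not depend on those numbers. For a pilot, this should be corrected before analysis, but it does not undermine the design.

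**What to change.** Amend the missing-data text in the Analysis section as follows.

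1. Drop the MCAR/MAR/MNAR classification as the trigger for the method. Keep the planned description of missingness and of those lost to follow-up.
2. Name one primary analysis under a stated MAR assumption: either the planned multilevel model using all observed midline and endline scores and baseline predictors of missingness, or multiple imputation.
3. Commit to a delta-adjusted or tipping-point sensitivity analysis by arm, whatever the missing-data assessment shows. Set the delta range in the SAP; closure data can help inform it.
4. In the planned flow diagram, count families excluded by the 10-week or two-timepoint rules separately from those with missing outcomes, by arm, so that the share exposed to this problem is visible.

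The cost is a wording change and modest extra analysis time. No new data are needed.
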